#### **End-of-study visit**

This will be the same as the end-of-cycle visit for the fourth injection cycle (above). Subjects who withdraw, or are withdrawn, prematurely from the study will be requested to attend for this final examination.

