#### 12.1.1 Safety

#### Subjects in age group 6-17 years

To generate a database with long-term safety data large enough to fulfill the requirements set out in the ICH E1 guideline (at least 100 subjects treated over one year) and taking into account an anticipated drop-out rate at least 144 subjects have to be included in the NT 201 group.

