# Safety Evaluation Set OLEX

The safety evaluation set (SES) of the OLEX period is the subset of all subjects who received study medication (NT 201) at least once during the OLEX period of the study.

If subjects have erroneously been treated with placebo during single OLEX cycles, no safety data in the respective cycle will be displayed. For summaries of safety data of the whole OLEX period or tables displaying changes between single cycles, for example shift tables, all subjects who received placebo in single OLEX cycles will be excluded. In case the OLEX period will be analyzed respective of MP treatment group, the actual treatment in MP will be used for safety data. For efficacy data subjects erroneously treated with placebo during single OLEX cycles will be included. Furthermore, the randomized/ assigned treatment in MP will be used for analysis respective of MP treatment group in chapter 14.1 and 14.2.

In the subject data listings, the treatment group of MP/OLEX will be listed as randomized/ assigned except for the section 16.2.7 and 16.2.8, here the actual treatment group of the respective cycle will be listed. All listings will be sorted by site, treatment group, subject and cycle.

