#### 6.5.3 Other safety variables

- Occurrence of non-treatment emergent AEs.
- Occurrence of non-serious TEAEs per period.
- Occurrence of TEAEs by worst intensity per period and injection cycle.
- Occurrence of TEAEs by worst causal relationship per period and injection cycle.

- Occurrence of related serious TEAEs per period and injection cycle.
- Occurrence of TEAEs by worst outcome per period and injection cycle.
- Listing of all serious TEAEs of subjects who died per period.
- Listing of TEAEs of standard MedDRA query suicide/self-injury and of TEAEs with possibly suicidal events, per period.
- Vital signs (blood pressure, heart rate, body temperature) at study baseline, V3 (week 4), V6 (week 16), during the main period, at injection visits in the extension period, at end of cycle visits in the extension period and at the end-of-study visit (V18) (Week 64).
- Body height and body mass index (BMI), calculated from body weight and height, at study baseline, final visit of the main period (V6) (Week 16), and end-of-study visit (V18) (Week 64).
- Body weight at study baseline, final visit of the main period (V6) (Week 16), at injection visits in the extension period, at end-of cycle visits in the extension period and end-of-study visit (V18) (Week 64).
- Clinical chemistry (including alkaline phosphatase (AP) and blood glucose (BG)) and hematology at study baseline, final visit of the main period V6 (Week 16), and end-of-study visit V18 (Week 64).
- Occurrence of antibodies against BoNT-A in subjects with  $\geq$  30 kg body weight.
- The number of subjects with suicidal ideation, suicidal behavior, and self-injurious behavior without suicidal intent during treatment based on the Columbia-Suicide Severity Rating Scale (C-SSRS).

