In general values measured at the baseline injection visit (V2) will be used as study baseline value. If data is missing for this visit the last valid value before first injection will be used instead. If e.g. the uSFR is not measured at Visit 2 (Baseline) and the last valid value before first injection is the uSFR value at screening then this value will be used as study baseline value in all analyses described below.

For all MP and OLEX tables the treatment groups will be analyzed as randomized/ assigned in the respective study period. For all OLEX tables, which are stratified by visit/cycle, only subjects with injection in the respective cycle are included; for the end-of-study visit all subjects with at least one injection in the OLEX are included (irrespective of regular or premature discontinuation). Additional to "End of Study" visit "Cycle 4 Week 16" visit will be analyzed. For "Cycle 4 Week 16" only subjects regularly completing cycle 4 are included. In general, percentages will be based on all subjects treated in the respective cycle.

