# 7.5 Safety Variables

The safety variables will be analyzed for the SES of the MP or OLEX by using descriptive summary statistics, frequency tables, and shift tables where appropriate.

All analyses will be performed by age groups and treatment and additionally for the group of subjects of all ages (2-17) who received NT 201 in the respective treatment period (main or extension period), i.e. all analyses of the MP will be stratified by "Placebo (6-17 years)", "NT 201 (6-17 years)", "NT 201 (2-5 years)", "Total NT 201 (2-17 years)". For the OLEX, two sets of tables will be produced: one "respective of main period treatment" showing "NT 201 (MP=Placebo, 6-17 years)", "NT 201 (MP=NT 201, 6-17 years)", "NT 201 (MP=NT 201, 2-5 years") and another set "irrespective of main period treatment" showing "NT 201 (6-17 years)", "NT 201 (2-5 years)" and "NT 201 (2-17 years)". OLEX tables for non-serious TEAEs with incidence  $\geq$  5%, C-SSRS and Botulinum toxin antibody results will only be presented irrespective of main period treatment.

For all OLEX tables which are stratified by visit/cycle, only subjects with injection in the respective cycle are included. For End of Study all subjects from SES (OLEX) will be included and the results from V18 will be used. Visit "Cycle 4 Week 16" will not be analyzed.

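### The by-visit extension safety tables pool cycle-4 completers with early leavers at V18 (Week 64) and omit the completers-only row that the SAP provides for efficacy

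*SAP*

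**What the plan says.** For the by-visit safety tables of the extension, SAP 7.5 gives two rules. The first sets the last row: "For End of Study all subjects from SES (OLEX) will be included and the results from V18 will be used". The second removes the alternative: "Visit 'Cycle 4 Week 16' will not be analyzed". Membership of the extension safety set is wide, being the "subset of all subjects who received study medication (NT 201) at least once during the OLEX period of the study" (SAP 5), so a child who stopped after the second injection belongs to it.

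SAP 6.5.3 defines the safety variables at the "end-of-study visit (V18) (Week 64"). The protocol makes that visit the same as the end-of-cycle visit of cycle 4, and adds: "Subjects who withdraw, or are withdrawn, prematurely from the study will be requested to attend for this final examination" (Protocol 6.1.2, End-of-study visit).

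SAP 7.1 handles the same visit differently for efficacy. In its End of Study row, "all subjects with at least one injection in the OLEX are included (irrespective of regular or premature discontinuation"). It then adds a 'Cycle 4 Week 16' row in which "only subjects regularly completing cycle 4 are included". Neither SAP 7.5 nor the list of changes in SAP 8 gives a reason for leaving that row out of the safety tables.

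**The concern.** A value described as V18 (Week 64) can come from a child who completed four cycles or from a child examined on leaving in cycle 2 or 3. The two differ in time since baseline and in number of injections. Growth measures depend on time. Laboratory values and antibodies may depend on cumulative exposure.

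The extension exists to provide safety data after repeated treatment. Protocol 6.2 refers to at least 100 children followed for one year, at least 50 of them consistently on the high dose through four injections. For variables measured in the extension only at V18, no planned summary isolates the children who reached the end of cycle 4.

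**Working it through.** **Inputs**
- Cycle length 16 ± 2 weeks, four cycles, total 64 weeks with a range of 56–72 (Protocol 6.1.1 and 8.2.4).
- Fourth injection at Week 48 (Protocol 8.2.4), so injections fall nominally at Weeks 0, 16, 32 and 48.
- Final visit after discontinuation: 16 ± 2 weeks after the last administration (Protocol 10.1). Protocol 9.2 describes the exit visit without a time. SAP 7.6 lets a discontinued cycle end at the last available visit and tabulates cycles under 14 weeks.
- Drop-out: no rate is given. Protocol 12.1.1 says "at least 144 subjects have to be included in the NT 201 group" in order to have at least 100 treated over one year.

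**Step 1: the plan's own schedule.** 4 × 16 = 64, 4 × 14 = 56 and 4 × 18 = 72 weeks. This reproduces the stated 64 (56–72).

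**Step 2: how far an early leaver is from Week 64.**

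| Last injection | Exit visit under Protocol 10.1 | Gap to Week 64 | Gap if examined right after that injection |
|---|---|---|---|
| 2nd (Week 16) | Week 32 | 32 weeks | 64 − 16 = 48 weeks |
| 3rd (Week 32) | Week 48 | 16 weeks | 64 − 32 = 32 weeks |
| 4th (Week 48) | Week 64 | 0 weeks | 64 − 48 = 16 weeks |

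With visit windows, the widest spread between two children under the Protocol 10.1 timing is 72 − 28 = 44 weeks.

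**Step 3: which tables are affected.**
- Clinical chemistry, hematology, height and BMI have V18 as their only extension time point (SAP 6.5.3).
- Antibodies are compared from baseline to V18, with V17 as a substitute (SAP 7.5).
- Vital signs and weight also have injection-visit and end-of-cycle time points in the extension, limited to children injected in that cycle.
- TEAE tables run by cycle and period, and C-SSRS tables by period. Neither uses the End of Study row.

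**Step 4: share of leavers in the row (assumption).** If 144 enter and 100 remain, at most 44 leave (44/144 = 30.6%). Spread evenly over four cycles, that is 11 per cycle. The 11 who leave in cycle 1 never receive an extension injection, so they cannot be in the row.
- Row size: 144 − 11 = 133
- Leavers in the row: 33/133 = 24.8%
- Leavers with fewer than four cycles: 22/133 = 16.5%

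**Step 5: dilution of a change linear in time.** Understatement = share of leavers × (64 − mean exit week)/64.
- Main case, exit at Weeks 32, 48 and 64 (mean 48): 0.248 × 16/64 = 0.062, about 6%. The mean week of the row is (100 × 64 + 33 × 48)/133 = 60.0.
- 10% leavers, same timing: 0.10 × 16/64 = 0.025, or 2.5%.
- 25% leavers examined at withdrawal, evenly over Weeks 16–64 (mean 40): 0.25 × 24/64 = 0.094, about 9%.

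**The case against.** An End of Study row that contains every exposed child is proper for safety, because it keeps those who left on account of harm. A completers-only row is a selected group. SAP 7.5 states its rule openly and calls the row End of Study. The Week 64 wording comes from the variable definition in SAP 6.5.3, and the table shells in SAP Appendix 1 are not available, so the printed label is not known. All of this stands. It argues for keeping the pooled row, not for dropping its companion.

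The extra row would not be fully homogeneous either. Children who start on placebo complete with three NT 201 injections (Protocol 6.2), and the antibody tables of the extension are produced only irrespective of main-period treatment (SAP 7.5). That also stands and is taken into the fix.

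Three stronger readings are tempting, and the documents do not support them.
- *All safety tables lose the end-of-cycle-4 information.* They do not. The primary and secondary safety variables are TEAE occurrences, reported by cycle with a separate definition for the fourth.
- *Early leavers are examined 48 weeks too soon.* That needs an examination directly after injection 2. The one explicit timing rule, in Protocol 10.1, gives 32 weeks nominally. Protocol 9.2 and SAP 7.6 leave earlier visits possible but do not prescribe them.
- *A linear change is understated by 11%.* This comes from 0.306 × 24/64 = 0.115, which counts main-period leavers who can never be in the row and assumes exit at withdrawal. Also, the exit visit is only requested, and leavers who do not attend contribute no V18 value.

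**Conclusion.** The point holds for the by-visit extension safety tables. SAP 7.5 pools completers and early leavers at a visit defined as Week 64, and expressly omits the row with which SAP 7.1 separates them for efficacy. The loss is greatest for clinical chemistry, hematology, height, BMI and antibodies, and smaller for vital signs and weight.

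The numerical effect is modest: about 6% understatement of a linear change in the main case, with 2.5% to about 9% across the other scenarios. These figures rest on an unstated drop-out rate, taken at the largest value that still leaves 100 of 144. They also assume even leaving, a change linear in time, and the same leaving pattern in placebo starters and in the youngest children, who are in the row but not in the 144. Linearity suits growth best. The documents give no basis for it for laboratory values or antibodies.

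No confirmatory result and no adverse-event conclusion is affected. This is a low-cost improvement in readability, not a flaw that threatens the trial.

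**What to change.** In SAP 7.5:
1. Delete the sentence that excludes 'Cycle 4 Week 16'.
2. Keep the all-subjects row and label it 'End of Study / last visit', without Week 64.
3. Add the 'Cycle 4 Week 16' row as already defined in SAP 7.1, for children regularly completing cycle 4, at least for clinical chemistry, hematology, height, BMI, weight, vital signs and antibodies.
4. Read the new row by main-period treatment where such tables exist. For antibodies, split the row the same way, or add a footnote that it mixes children with three and four NT 201 injections.

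The cost is one descriptive row per table, from data already collected and a definition already written. Because the completers' row is selective, it should supplement the all-subjects row and not replace it.

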#### Adverse Events

AEs will be coded according to the Medical Dictionary for Regulatory Activities (MedDRA) (version in effect when the database is closed).

TEAEs of MP are defined as AEs with onset or worsening after the first injection of NT 201 or Placebo up to and before first injection of the extension period or - in case of discontinuation before second injection – up to and including 16 weeks after first injection of NT 201 or Placebo or date of last study visit, whichever is later. AEs starting in the MP and not having resolved at the final visit of MP (V6) will be followed and further documented in the extension period.

TEAEs of OLEX are defined as AEs with onset or worsening after the first injection of OLEX up to and including 16 weeks after last injection or the date of last study visit, whichever is later.

A detailed description of the rules to be used for the classification of TEAEs can be found in Appendix 1. If an AE worsens between start and end of this AE it will be considered as new AE starting with the date of the worsening. In this case the imputation of end dates within episodes of the same AE will be done by setting the end date/end time to start date/start time of the consecutive worsening record.

In detail missing or partially missing start and stop dates of an AE will be imputed as follows for the calculation of the duration of an AE:

Page 26 of 46

- if start time is missing and date is given and not equal to first exposure date in MP or OLEX, set time to 00:00, else if date is equal to first exposure date in MP or OLEX set time to time of first exposure in MP or OLEX, if given (else 00:00), respectively
- if start time is missing and date is given and equal to the subsequent exposure date in OLEX (e.g. 2nd injection in OLEX), set time to time of the subsequent exposure, if given (else 00:00)
- if start date/time is completely missing and end date is not after or equal to first exposure of MP: no imputation.
- if start date/time is (partially) missing and end date is after or equal first exposure in MP or missing:
  - $\circ$  only start day is missing, but month and year same as first exposure in MP or OLEX: set day and time to day and time of first exposure, else set day to 1 and time to 00:00
  - Start day and month are missing, but year is the same as year of first exposure in the MP (which is ≠ year of first exposure in OLEX): set day, month, time to day, month, time of first exposure in the MP
  - Start day and month are missing, but year is the same as year of first exposure in the OLEX (which might be the same as year of first exposure in MP): set day, month, time to day, month, time of first exposure in OLEX
  - Start day and month are missing and year is not the same as year of first exposure in the MP or OLEX: else set day and month to 1 and time to 00:00
- if start date/time is completely missing and end date/time is at or after date/time of first exposure in the MP and before date/time of first exposure in OLEX, set start date/time to date/time of first exposure in the MP (e.g. AE start missing, AE end date 10CT2014, first injection MP: 1AUG2014).
- if start date/time is completely missing and end date/time is at or after date/time of first exposure in the OLEX, set start date/time to date/time of first exposure in the OLEX
- if AE end date and time are missing and date and time of study end (i.e. last contact or last visit of the study) are not missing, set end date/time to study end date/time, else set end date to study end date and time to 23:59.
- if AE end date/time is partially missing and given information on date is not equal to study end, set day to last day of the given month or day/month to 31/12 of the given year and missing time to 23:59.
- if AE end date/time is partially missing and year or year and month are equal to year or year and month of study end, set analysis end date/time to the date/time study end and missing time to 23:59.
- if AE end time is missing time will be set to 23:59
- if start date and end date is completely missing, set end date to study end date and time to 23:59. Estimate then missing start date as described above

In the following case a special rule will be applied:

If it is not clear in which OLEX cycle the AE starts, incomplete AE start dates/times will be replaced in such a way that the AE is assigned to the earliest possible cycle:

- if start time is missing but date is given and equal to any exposure date in OLEX and AE is assigned to the later cycle, time will be set to start of the later cycle. If AE is assigned to the previous cycle, time will be set to 0:00.
- If day and time are missing, but month and year are given and equal to any exposure date (month and year) in OLEX and AE is assigned to the later cycle, day and time will be set to start day and time of the later cycle. If AE is assigned to the previous cycle, day will be set to 1 and time to 00:00.
- If month, day and time are missing, but year is given and covering several OLEX cycles and the earliest possible OLEX cycle for assignment starts in the year before the AE start (but ends in the year of the AE start), month and day will be set to 1 and time to 00:00. If the earliest possible OLEX cycle for assignment starts in the year of the AE start, month/day/time will be set to month/day/time of the respective cycle start.

Calculation of time to duration of AEs [days]:

• The duration will be calculated as stop date - onset date + 1 for each episode of worsening of AE.

An overview summary table will be created for TEAEs and non-TEAEs displaying the frequencies and percentages of the following categories: "Any TEAE", "Any TEAE related to treatment", "Any TEAE of special interest", "Any TEAE of special interest related to treatment", "Any serious TEAE", "Any serious TEAE related to treatment", "Any TEAE leading to discontinuation", "Any TEAE leading to discontinuation related to treatment", "Any fatal TEAE" and "Any fatal TEAE related to treatment" for TEAEs and "Any non-TEAE", "Any non-TEAE", "Any serious non-TEAE", "Any non-TEAE", "Any serious non-TEAE", "Any non-TEAE leading to discontinuation" and "Any fatal non-TEAE" for non-TEAEs.

Incidences will be calculated for TEAEs, treatment-related TEAEs, serious TEAEs, related serious TEAEs, TEAEs leading to discontinuation, TEAEs of special interest at the system organ class level and at the preferred term level and will be presented by treatment, by injection cycle and overall (i.e. per period). TEAEs will also be presented by preferred term level, by treatment, injection cycle and overall. Additionally, TEAEs will be analyzed by worst intensity, by worst causal relationship and by worst outcome.

The number and percentage of subjects with at least one non-serious TEAE with incidence  $\geq =$  5% will be displayed by system organ class level and preferred term level.

In general, all safety analyses for OLEX will be performed overall and for the  $2^{nd}$ ,  $3^{rd}$  and  $4^{th}$  injection cycle. Only the number and percentage of subjects with at least one non-serious TEAE with incidence  $\geq = 5\%$  will be performed overall only.

Listings displaying incidences for TEAEs leading to discontinuation, serious TEAEs and TEAEs of special interest will also be provided.

Listings will be created for subjects who died, subjects with TEAEs of standard MedDRA query suicide/self-injury and for subjects with possibly suicidal events.

TEAEs for the  $2^{nd}$  injection cycle are defined as adverse events with onset or worsening at or after date of  $2^{nd}$  injection and before date of  $3^{rd}$  injection. TEAEs for the  $3^{rd}$  injection cycle are defined as adverse events with onset or worsening at or after date of  $3^{rd}$  injection and before date of  $4^{th}$  injection. TEAEs for the  $4^{th}$  injection cycle are defined as TEAEs with onset or worsening at or after 4th injection.

Duration of AEs will be listed only. Imputed values will be flagged as such.

In case of missing intensity or missing causal relationship of an AE the worst case principle will be applied, i.e. a missing intensity will be set to "severe" and a missing causal relationship will be set to "related". Missing data of the worst outcome will be imputed by "unknown". If a subject has more than one outcome within a preferred term (PT) only the worst outcome will be used in the frequency tables. Also on subject level only the worst outcome is defined in the following order:

- recovered/resolved
- recovered/resolved with sequelae
- recovering/resolving
- not recovered/not resolved
- unknown
- fatal.

For any missing data on seriousness a worst case strategy will be applied for all analysis tables. The AE will be regarded as 'serious'.

TEAESIs are defined as adverse events occurring after treatment that are thought to possibly indicate toxin spread. The list of adverse events of special interest possibly indicating toxin spread based on MedDRA version 22.0 (version in effect at database closure) is given in Table 4.

MedDRA Preferred Term (MedDRA version 22.0)		
Accommodation disorder	IIIrd nerve paresis	
Areflexia	Ileus paralytic	
Aspiration	IVth nerve paresis	
Botulism	Monoparesis	
Bradycardia	Muscular weakness	
Bulbar palsy	Paralysis	
Constipation	Paraparesis	
Cranial nerve palsies multiple	Paresis	
Cranial nerve paralysis	Paresis cranial nerve	
Diaphragmatic paralysis	Peripheral nerve palsy	
Diplopia	Peripheral paralysis	
Dry mouth: only when severe, serious, or outcome is not recovered, fatal or unknown	Pelvic floor muscle weakness	
Dysarthria	Pneumonia aspiration	
Dysphagia	Pupillary reflex impaired	
Dysphonia	Quadriparesis	
Dyspnoea	Respiratory arrest	
Extraocular muscle paresis	Respiratory depression	
Eyelid function disorder	Respiratory failure	
Eyelid ptosis	Speech disorder	
Facial paralysis	Trigeminal nerve paresis	
Facial paresis	Urinary retention	
Hemiparesis	Vision blurred	
Hypoglossal nerve paresis	Vocal cord paralysis	
Hyporeflexia	Vocal cord paresis	
Hypotonia		
Wording of preferred terms is according to MedDRA version 22.0		

Table 4: List of Adverse	Events of Special	Interest Possibly I	ndicating Toxin Spread
Table 4. List of Auverse	Events of Special.	Interest I ussibly II	nuicating Toxin Spicau

To fulfill FDA requirements, TEAE data will be screened for suicidal events. The MedDRA Preferred Terms of all TEAEs will be checked using standard MedDRA query (SMQ) 'Suicide/self-injury'. Resulting TEAE findings will be listed in a separate listing. A list of the MedDRA Preferred Terms of the SMQ 'Suicide/self-injury' based on MedDRA version 22.0 is given in Table 5 (version in effect at database closure).

MedDRA Preferred Term:	MedDRA Preferred Term:	
Assisted suicide	Self-injurious ideation	
Columbia suicide severity rating scale abnormal	Suicidal behaviour	
Completed suicide	Suicidal ideation	
Depression suicidal	Suicide attempt	
Intentional overdose	Suicide threat	
Intentional self-injury	Suspected suicide	
Poisoning deliberate	Suspected suicide attempt	
Wording of preferred terms is according to MedDRA version 22.0		

In addition all comment fields of the case report form (CRF) and all investigator reported terms of TEAEs will be screened for the following terms or term elements ('strings') and listed in a separate listing:

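### SAP 7.5: the main-period and extension TEAE windows leave out the exact injection time, where untimed injection-day AEs are imputed, and cycles 2 and 3 have no end rule for a child with no further injection

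*SAP*

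**What the plan says.** All the rules below are in SAP 7.5, Adverse Events.

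- **MP window.** "TEAEs of MP are defined as AEs with onset or worsening after the first injection of NT 201 or Placebo up to and before" the first injection of the extension period. For a child who discontinues before a second injection, the window runs "up to and including 16 weeks after first injection of NT 201 or Placebo or date of last study visit, whichever is later".
- **OLEX window.** "TEAEs of OLEX are defined as AEs with onset or worsening after the first injection of OLEX". It closes at the later of two dates: 16 weeks after the child's final injection, and the last study visit.
- **Missing start time.** On the day of the first MP or first OLEX injection the rule is: "else if date is equal to first exposure date in MP or OLEX set time to time of first exposure in MP or OLEX", or 00:00 if that time is not given. On a later OLEX injection day the start takes the time of that injection. If only the start day is missing, and month and year match the first MP or OLEX exposure, day and time are set to those of that exposure.
- **Purpose of the imputation.** Dates and times "will be imputed as follows for the calculation of the duration of an AE". A further rule covers AEs whose OLEX cycle is unclear and assigns them to the earliest possible cycle.
- **Cycle windows.** TEAEs for cycles 2 and 3 "are defined as adverse events with onset or worsening at or after date of" the injection that opens the cycle, and must precede the date of the next injection. Cycle 4 starts at or after the fourth injection and has no upper limit.
- **Classification detail.** The section refers to Appendix 1 for the detailed TEAE classification rules. That appendix is a separate file and was not available here.

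**The concern.** Two parts of the same section do not fit together. The period definitions exclude the instant of injection, and the imputation rule places untimed injection-day onsets at that instant. The cycle definitions do include it, so an AE can belong to cycle 2 without belonging to the OLEX period that contains cycle 2.

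The cycle 2 and 3 windows also close only at a next injection. A child who stops in one of these cycles has no such date, and nothing says where the window then ends.

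The events at stake matter. Occurrence of TEAEs overall and by injection cycle is the primary safety variable (SAP 6.5.1), and TEAEs leading to discontinuation by cycle are secondary (SAP 6.5.2). Injection-day events are actively sought: protocol 9.1.1.3 requires at least two hours of on-site observation for bleeding, pain and swelling, which are among the local risks listed in protocol 4.3. The list of AE items in protocol 10.1 gives onset as a date and names a time only for resolution. Severe respiratory or swallowing AEs of special interest end further injections (protocol 7.5.1), so some of the most important events occur in children who have no next injection.

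**Working it through.** The SAP gives no figure for this point, so the rules are applied to example records.

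**Notation.** I1 to I4 are the injection date-times, V is the last study visit and t is the AE start. Sixteen weeks are 16 × 7 = 112 days. Periods are compared by date-time, and cycles 2 and 3 by date, as their wording indicates.

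- MP: t > I1 and t < I2; without I2, t ≤ max(I1 + 112, V)
- OLEX: t > I2 and t ≤ max(last injection + 112, V)
- Cycle 2: date(t) ≥ date(I2) and date(t) < date(I3); cycle 3 likewise with I3 and I4
- Cycle 4: t ≥ I4

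**Example.** Injections at 09:00 (0.375 of a day) on days 0, 112, 224 and 336.

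**A. AE on an injection day, no clock time, start imputed to the injection time**

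| Injection | t | MP | OLEX | Cycle window met |
|---|---|---|---|---|
| 1 | 0.375 | no (0.375 > 0.375 is false) | no | none of cycles 2 to 4 |
| 2 | 112.375 | no (112.375 < 112.375 is false) | no (112.375 > 112.375 is false) | 2 |
| 3 | 224.375 | no | yes | 3 |
| 4 | 336.375 | no | yes | 4 |

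So 2 of the 4 injection days fail at period level, and 1 of the 4 (injection 1) fails everywhere. With a recorded onset one hour after injection, none fails. A start with only the day missing, in the month of first MP or OLEX exposure, also gets t = I1 or t = I2 and behaves like row 1 or 2.

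If the earliest-cycle rule sets the time to 00:00 instead, the result changes but is still inconsistent. At injection 2 (t = 112.0) the AE is in both MP and cycle 2. At injection 4 (t = 336.0) it is in OLEX but in no cycle, because its date is not before the date of injection 4 and its time is not at or after it.

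**B. AE 10 days after the last injection, last visit 30 days after it**

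| Child stops after | Period | Cycle, missing next date read as a failed comparison | Cycle, window read as open-ended |
|---|---|---|---|
| injection 1 | MP | not applicable | not applicable |
| injection 2 | OLEX (122.375 ≤ max(224.375, 142.375)) | none | 2 |
| injection 3 | OLEX (234.375 ≤ max(336.375, 254.375)) | none | 3 |
| injection 4 | OLEX | 4 | 4 |

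The failed comparison assumes a direct SAS test of the AE date against a missing next-injection date. SAS orders a missing value below every date, so the test is false. The SAP specifies SAS 9.4 (section 2) but gives no code for TEAEs.

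**After the change.** With *at or after*, 0.375 ≥ 0.375 puts row 1 of table A in MP, and 112.375 ≥ 112.375 puts row 2 in OLEX. With the discontinuation clause in cycles 2 and 3, the AEs at 122.375 and 234.375 fall in cycles 2 and 3 whichever way a missing date is read.

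**The case against.** **Appendix 1 governs classification.** The section sends the reader there, and it may place these records correctly. This limits what can be said about the final tables. It does not repair the main text: SAP section 2 says the plan should be precise enough to guide programming, and a correct appendix would then contradict the stated windows.

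**The imputation is introduced for duration, not TEAE status.** That is its stated purpose. But SAP 7.5 counts duration in whole days, as stop date minus onset date plus one, so an imputed clock time cannot change it. The earliest-cycle rule also ties imputed starts directly to cycle assignment. The objection is fair but weak.

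**The SAP says elsewhere where a discontinued cycle ends.** SAP 7.6, Duration of exposure, uses the last available visit. This shows the likely intent, but it defines cycle length and is not carried into the TEAE definitions.

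**The loss is limited.** This stands. Non-TEAEs are also tabulated, the rules are the same in both arms, and cycle 2 and 3 AEs of children who stop remain in the OLEX totals.

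A reader might infer more than the documents support:

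- *All TEAE windows miss untimed injection-day AEs.* They do not. Cycles 2 to 4 are written at or after, and AEs imputed to injections 3 and 4 are inside OLEX.
- *TEAEs leading to discontinuation must be zero in cycles 2 and 3.* Cycle is assigned by onset or worsening. An AE starting in cycle 2 can lead to discontinuation after the third injection, and it then meets the cycle 2 window.
- *Missing onset times are usual.* The protocol list does not exclude an onset time, and the SAP treats a missing one as a case for imputation. How often it is missing is unknown.

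**Conclusion.** The inconsistency is real but narrow. On the main text, an AE imputed to the time of injection 1 is in no TEAE window. One imputed to the time of injection 2 is a cycle 2 TEAE but is absent from both the MP and the OLEX totals. Injection 1 opens the placebo-controlled period, so that part touches the between-arm comparison of the primary safety variable. It does so under the same rule in both arms.

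For cycles 2 and 3, the end of the window is undefined for a child with no further injection. By-cycle counts lose such AEs under a literal comparison and keep them under an open-ended reading, so two programmers could produce different tables from the same text. OLEX totals are unaffected.

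The number of AEs affected cannot be derived. The planned enrolment of 249 is a count of children, not of affected AEs. The safety sample size (at least 100 treated for a year out of 144) allows for up to 44/144 = 30.6% leaving early, but that covers all cycles and says nothing about AEs, so it is only an outer frame.

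The conclusion assumes that the imputed start decides TEAE status, that the period windows are compared by date-time, and that Appendix 1 does not already resolve the matter.

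**What to change.** In SAP 7.5:

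1. Define MP TEAEs as onset or worsening *at or after* the first injection and before the first OLEX injection, and OLEX TEAEs as *at or after* the first OLEX injection.
2. End cycles 2 and 3 at the next injection or, if there is none, at the later of 16 weeks after that cycle's injection and the last study visit. This carries over the clause the period definitions already use.
3. Check that Appendix 1 states the same rules. In the same check, settle whether cycle boundaries are compared by date or by date-time, because items 1 and 2 alone do not resolve the 00:00 branch of the earliest-cycle rule.

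The cost is a few sentences of SAP text and a check of the appendix, with no new data. The downside is that an untimed AE that began before the injection on the same day is counted as treatment-emergent, which is the conservative direction for safety.
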